COVER PAGE

Official title of the study: Efficacy of Gluma desensitizer in controlling the immediate post treatment sensitivity in etch-and-rinse and self-etch adhesive occlusal composite restorations

NCT04248803

Date of the document: 02-09-2025

Efficacy of Gluma desensitizer in controlling the immediate post treatment sensitivity in etch-and-rinse and self-etch adhesive occlusal composite restorations

NCT04248803

BRIEF SUMMARY

Background

One of the most widely used esthetic restorations in dentistry is composite. Despite the indispensable value that composite brings to a dentist's arsenal, the postoperative sensitivity following composite resin restorations are an undesirable outcome often leading to patient discomfort.

GLUMA desensitizer, a solution containing glutaraldehyde and hydroxyethyl methacrylate (HEMA), is widely used to reduce sensitivity by occluding dentinal tubules and stabilizing collagen fibrils. However, the ideal timing of GLUMA application in different adhesive protocols remains uncertain, raising questions about its effect on postoperative sensitivity, adhesive bond strength, and long-term restoration success.

This clinical trial aims to evaluate the effectiveness of GLUMA in controlling the immediate post treatment sensitivity following occlusal composite restorations. In addition, to compare the difference between the bonding systems (Etch-and-rinse & Self-etch) on reduction of post restoration sensitivity with or without Gluma desensitizer.

Sample Size, Blinding and Randomization

For this clinical trial, a sample size of 504 restorations was calculated to be sufficient for detecting statistical difference using G* power software (α probability error – 0.05 and effect size – 0.2).

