The primary outcome of this clinical trial is to evaluate the effectiveness of GLUMA in controlling the immediate post treatment sensitivity following occlusal composite restorations. Hence, all the patients were assessed for post restoration sensitivity after 24 hours, 48 hours and at the end of one week. The secondary outcome was to assess whether patient had post-operative sensitivity due to any trigger stimulus. This was also assessed at the end of 24 hours, 48 hours and one week post-operatively.

Post-operative sensitivity and trigger factors (if any) after 24 and 48 hours were assessed with VAS score (1- 10) through telephonic call by a resident student who are unaware of the treatment allocation group. In this study a 1-10 scale were used and the patient is asked to choose a number ranging from 1 to 10 based on their sensitivity, with 1 being the least sensitivity and 10 being the most.

Post-operative sensitivity and trigger factors (if any) after one week were checked by recalling and clinically assessing the patients using Schiff cold air sensitivity scale by a blinded EPGS.

Statistical Analysis

Data was assessed (IBM SPSS Version 23, USA) for normality using the Shapiro-Wilk test. Non-parametric Kruskal-Wallis test and Mann Whitney U test are employed for difference in post treatment sensitivity score among the different groups.

DETAILED DESCRIPTION

Introduction One of the most widely used esthetic restorations in dentistry is composite. Despite the indispensable value that composite brings to a dentist's arsenal, the postoperative sensitivity following composite resin restorations are an undesirable outcome often leading to patient discomfort. ¹This sensitivity

is primarily caused by dentinal fluid movement within exposed tubules, which can be exacerbated by adhesive protocols that do not adequately seal the dentin (Pashley *et al.*, 2002)², micro gaps caused by polymerization shrinkage (Loguercio *et al.*, 2004)³, dentin desiccation and bond degradation over time, potentially due to matrix metalloproteinase (MMP) activation (Mazzoni A *et al.*, 2015)⁴. It's been reported that during the first week after placement of Class I posterior composite restorations, 23% of the patients experienced post-operative sensitivity.⁵

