Intervention description for **Arm 4: Self Etch Control group (No desensitizer application)** where no desensitizer was applied after preparing the cavity two coats of Universal adhesive (3M ESPE Single Bond Universal Adhesive, Germany) were applied by scrubbing with a micro brush, for 20 s per coat. When the surface became shiny, it was light-cured for 20s (Woodpecker LED, Guilin, China). After curing the adhesives, placement of Composite (Charisma Smart, Kulzer GmbH, Germany in increments (1–2 mm thick) by layering technique to reduce polymerization shrinkage.

Intervention description for **Arm 5: Self Etch Gluma desensitizer application prior to etching** in this group a small amount of Gluma Desensitizer (Kulzer GmbH, Germany) was applied to the prepared dentin surface for 30-60 seconds, and then gently dried with air until the surface is no longer shiny. Finally, rinse thoroughly with water and suction. Followed by two coats of Universal adhesive (3M ESPE Single Bond Universal Adhesive, Germany) were applied by scrubbing with a micro brush, for 20 s per coat. When the surface became shiny, it was light-cured for 20s (Woodpecker LED, Guilin, China). After curing the adhesives, placement of Composite (Charisma Smart, Kulzer GmbH, Germany in increments (1–2 mm thick) by layering technique to reduce polymerization shrinkage.

Intervention description for **Arm 6: Self Etch Gluma desensitizer application after self-etch adhesive usage** two coats of Universal adhesive (3M ESPE Single Bond Universal Adhesive, Germany) were applied by scrubbing with a micro brush, for 20 s per coat. When the surface became shiny, it was light-cured for 20s (Woodpecker LED, Guilin, China). After curing the adhesives a small amount of Gluma Desensitizer (Kulzer GmbH, Germany) was applied to the prepared dentin surface for 30-60 seconds,

and then gently dried with air until the surface is no longer shiny. Finally, rinse thoroughly with water and suction. Placement of Composite (Charisma Smart, Kulzer GmbH, Germany in increments (1–2 mm thick) by layering technique to reduce polymerization shrinkage.

Outcome measures

The primary outcome of this clinical trial is to evaluate the effectiveness of GLUMA in controlling the immediate post treatment sensitivity following occlusal composite restorations. Hence, all the patients were assessed for post restoration sensitivity after 24 hours, 48 hours and at the end of one week.

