The Kruskal-Wallis test is a non-parametric statistical test used to determine if there's a significant difference between the medians of three or more independent groups. It's an alternative to the one-way ANOVA when the data doesn't meet the assumptions of normality or equal variances.

STATISTICAL ANALYSIS OVERVIEW:

This present study contains six arms whose descriptions have been provided in the brief summary. The statistical analysis was performed using IBM SPSS version 23. The normality was assessed using Shapiro – wilks test and Q -Q plots. Since the groups do not follow the normal distribution Kruskal – Wallis test to test the statistical significance of post operative sensitivity among the groups. Mann – whitney U test was used to assess the post operative sensitivity among the control groups.

GROUPS INVOLVED:

CONTROL GROUPS:

GROUP 1: Total Etch (TE) Control Group

GROUP 2: Self Etch (SE) Control Group

TEST GROUPS:

GROUP 2: TE - GLUMA Application After Acid Etching

GROUP 3: TE - GLUMA Application Prior to Acid Etching

GROUP 5: SE - GLUMA Application Prior to Acid Etching

GROUP 6: SE - GLUMA Application After Acid Etching

NULL HYPOTHESIS:

The null hypothesis states that there is no statistically significant difference in post operative sensitivity on GLUMA application etching before or after total etching or self-etching followed by composite restoration of the carious teeth.

SAMPLE SIZE CALCULATION:

For this clinical trial, a sample size of 504 restorations was calculated to be sufficient for detecting statistical difference using G* power software (α probability error – 0.05 and effect size – 0.2).

TYPE OF ANALYSIS:

The type of trial is a Noninferiority trials. By definition a non – inferiority trial tests whether a new experimental treatment is not unacceptably less efficacious than an active control treatment already in use. With continuous improvements in health technologies, standard care, and clinical outcomes, the incremental benefits of newly developed treatments may be only marginal over existing treatments. (Hahn S. Understanding noninferiority trials. Korean journal of pediatrics. 2012 Nov 23;55(11):403.)

This test is a non - inferiority trial hence the six groups have GLUMA application before etching of a composite restoration which is not unacceptably less efficacious in reducing post operative sensitivity in composite restoration of a carious tooth.

PROCEDURE:

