All statistical analyses were performed using non-parametric tests due to the non-normal distribution of the data, as confirmed by both the **Kolmogorov–Smirnov** and **Shapiro–Wilk** tests

($p < 0.001$). Descriptive statistics including mean and standard deviation (Mean \pm SD) were calculated for each of the six desensitizer groups at different time points: Pre-operative, 24 hours, 48 hours, and 1 week post-operative sensitivity, measured using the Visual Analog Scale (VAS).

For intergroup comparisons across all six desensitizer protocols, the **Kruskal–Wallis test** was used independently for each time point. This non-parametric method was selected to assess statistically significant differences in median VAS ranks among the groups, given the violation of normality assumptions. A separate p -value was generated for each time point:

- Pre-operative VAS: $p = 0.003$ (significant)
- 24-hour VAS: $p = 0.126$ (not significant)
- 48-hour VAS: $p = 0.050$ (borderline)
- 1-week VAS: $p = 0.013$ (significant)

Pairwise comparisons between the **Total-etch control** and **Self-etch control** groups were performed using the **Mann–Whitney U test**. This analysis revealed a statistically significant difference in pre-operative VAS scores ($p = 0.012$), while post-operative scores showed no significant differences at 24 hours ($p = 0.337$).

Mean pain scores (VAS) were also summarized for each group at all four-time intervals. The **self-etch Gluma prior to etching group consistently showed the lowest VAS scores** at all time points, suggesting reduced post-operative sensitivity in this group.

Given the minimal differences in outcome scores among the other groups, and the slightly better performance of the self-etch GLUMA prior to etching group, the data suggest that **most treatment protocols were non-inferior** to the best-performing group. Therefore, the trial was interpreted as

a **non-inferiority study**, evaluating whether the other etching and desensitizing protocols were not clinically worse than the most effective group.

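### The bonding-system aim is tested directly only between the two no-Gluma control arms at 24 hours: one of the nine matched post-operative contrasts that the aim implies

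*Combined protocol and SAP*

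**What the plan says.** The Brief Summary and the Detailed Description both give a second aim: "to compare the difference between the bonding systems (Etch-and-rinse & Self-etch) on reduction of post restoration sensitivity with or without Gluma desensitizer". Under Outcome measures, "all the patients were assessed for post restoration sensitivity after 24 hours, 48 hours and at the end of one week". The short Statistical Analysis paragraph in the Brief Summary does not restrict the tests to particular arms: "Mann Whitney U test are employed for difference in post treatment sensitivity score among the different groups".

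The SAP is narrower. Its Statistical Analysis Overview states that "whitney U test was used to assess the post operative sensitivity among the control groups". The Procedure section and the second Ranks table give that test at two times only: pre-operatively (p = 0.012) and at 24 hours (p = 0.337), where "post-operative scores showed no significant differences at 24 hours". The table has no 48-hour or 1-week row.

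For the six arms together, the Kruskal-Wallis test "was used independently for each time point". No post-hoc comparison, pooled bonding-system contrast or interaction is described. The only effect estimate is a 1-week mean difference of 0.18 between self-etch with Gluma before etching and total-etch with Gluma after etching.

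**The concern.** The six arms form a two-by-three layout: two bonding systems crossed with no Gluma, Gluma before and Gluma after. An aim that compares the systems with or without Gluma needs the system contrast at each Gluma level, and the outcome is taken at three times. The SAP examines the contrast at one level and one time.

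Two things are at stake. A reader may take the 24-hour control result (p = 0.337) as the answer for bonding systems in general, although it says nothing about the Gluma arms or the later times. Also, the aim concerns reduction, while the comparison made is of raw post-operative scores between two arms that already differed before treatment (means 0.86 and 1.88, p = 0.012).

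**Working it through.** **Inputs.** Arm sizes and mean ranks come from the two Ranks tables in the SAP; means and SDs come from the table that follows them. Arms are paired by their printed names. The blank 48-hour size for self-etch control is taken as 82. The 1-week column is taken as VAS, as labelled.

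**1. The plan's own figures.**
- The 0.18 estimate is 0.26 - 0.08 = 0.18, and its lower limit is 0.18 - 1.645 × 0.1077 = 0.003. Both reproduce. The two arms differ in bonding system and in Gluma timing, so the estimate isolates neither.
- The Mann-Whitney p-values cannot be reproduced exactly, because tie counts are not given. Without a tie correction, the printed mean ranks with 43 and 41 observations give 0.029 and 0.481 (printed: 0.012 and 0.337).

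**2. Coverage.** 3 matched pairs × 3 post-operative times = 9 contrasts; 1 is tested. Restorations used: 86 + 82 = 168, and 168/504 = 0.33.

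**3. Analysed number.** Ranks over N observations average (N + 1)/2.
- Six arms: the size-weighted mean rank is 126.5 at all four times. N = 504 requires 252.5; N = 252 gives 126.5.
- Two controls, pre-operatively: (86 × 36.83 + 82 × 48.45)/168 = 42.5. N = 168 requires 84.5; N = 84 gives 42.5.

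The one-third fraction survives, since 84/252 = 0.33. The counts do not.

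**4. The nine contrasts.** Difference = self-etch mean - total-etch mean; standard error = √(SD₁²/n₁ + SD₂²/n₂); Welch 95% CI at the printed sizes.

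| Time | No Gluma | Gluma before | Gluma after |
|---|---|---|---|
| Pre-operative | +1.02 (0.41, 1.63) | -1.09 (-1.59, -0.59) | +0.95 (0.25, 1.65) |
| 24 h | +0.29 (-0.08, 0.66) | -0.29 (-0.58, 0.00) | +0.33 (-0.03, 0.69) |
| 48 h | +0.04 (-0.27, 0.35) | -0.37 (-0.60, -0.14) | +0.09 (-0.21, 0.39) |
| 1 week | -0.09 (-0.27, 0.09) | -0.15 (-0.33, 0.03) | -0.05 (-0.29, 0.19) |

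The largest matched post-operative difference (Gluma before, 48 h; p = 0.002) has no directed test in the plan. With arm sizes halved it is -0.37 (-0.70, -0.04), p = 0.030, and every other post-operative contrast has p > 0.16.

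**5. Role of baseline.** At 24 h all three differences have the same sign as the pre-operative ones. Subtracting the pre-operative difference reverses each sign:
- No Gluma: 0.29 - 1.02 = -0.73
- Gluma before: -0.29 + 1.09 = +0.80
- Gluma after: 0.33 - 0.95 = -0.62

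A simple change score can over-correct, so these are not proposed as estimates. They show that the direction of the answer depends on how baseline is handled.

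**6. Pooling.** With equal weights the 24-hour difference is (0.29 - 0.29 + 0.33)/3 = +0.11 (-0.09, 0.31). This averages effects of opposite sign.

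**The case against.** The strongest reply is that the Gluma arms and later times are not ignored. Kruskal-Wallis covers all six arms at 24 hours, 48 hours and 1 week, and means, SDs and mean ranks are printed for each. That is correct, and a reader who inferred that these data were left out altogether would be wrong. What is missing is a directed contrast: p = 0.013 at 1 week says that some arms differ, not that the bonding systems do.

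A reader might also infer that the missing control results hide a reversal, since the means favour total-etch at 24 hours (0.37 against 0.66) and self-etch at 1 week (0.21 against 0.12). The documents do not support this on the rank scale that the SAP uses. In the six-arm rankings, total-etch control has the lower mean rank at 24 hours (125.47 against 136.49), at 48 hours (131.74 against 132.76) and at 1 week (124.24 against 129.76). The 1-week interval for the mean difference also includes zero.

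Nor does the 48-hour Gluma-before difference show that self-etch is better. Multiplied by nine for nine contrasts, p = 0.002 becomes 0.018 at the printed sizes, but p = 0.030 becomes 0.27 at half sizes. That pair also started 1.09 apart.

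Finally, the primary question is whether Gluma works, and the bonding-system comparison comes second. That limits the priority of the point, but it remains a stated aim.

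**Conclusion.** The concern holds as a gap between a stated aim and its analysis: one of nine matched post-operative contrasts is tested, on one third of the restorations, without allowance for a pre-operative difference in the same two arms. Neither the six-arm test nor the 0.18 estimate fills the gap. The coverage count rests only on the documents' text and tables.

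The contrasts in the working are illustrative. They assume that the printed means and SDs are right, use a mean-based method on skewed scores, and are unadjusted for baseline or multiplicity. They show that the control pair does not represent the Gluma pairs; they do not establish which bonding system is better, or that results were withheld. The point should be addressed before any general statement about bonding systems is made.

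**What to change.** 1. Reconcile the analysed number (504 and 168, or 252 and 84) and correct the tables.
2. Report self-etch against total-etch within each Gluma level (none, before, after) at 24 hours, 48 hours and 1 week, with estimates and intervals.
3. Add a baseline-adjusted rank-based or ordinal model at each time, with bonding system, Gluma timing and their interaction, using the pre-operative VAS already collected.
4. Give a pooled stratified estimate only beside the three stratum results.
5. Adjust for multiplicity, and label all of this post hoc, because the SAP already contains results.

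If this is not done, state that the bonding-system conclusion applies only to the no-Gluma arms at 24 hours.

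The cost is about a dozen further tests or estimates (nine contrasts and three models) on existing data, with wider intervals after multiplicity adjustment.

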A significance level of $p < 0.05$ was considered statistically significant throughout the analysis. In the present study, the Kruskal-Wallis test was used to compare six desensitizer groups at different time intervals (Pre-operative, 24 hours, 48 hours, and 1 week post-operatively) based on Visual Analog Scale (VAS) scores. Since each time point represents a distinct clinical endpoint, a separate Kruskal-Wallis test was conducted for each, yielding **individual p-values** corresponding to each time point. As the Kruskal-Wallis test does not permit aggregation of multiple outcomes into a single p-value, **a common p-value is not statistically appropriate**.

Ranks

	Desensitizer Group	N	Mean Rank	P Value ^a
Pre Op VAS	Total etch control	86	105.48	0.003
	Total etch Gluma prior to etching	94	141.70	
	Total etch Gluma after etching	86	116.12	
	Self etch control	82	142.30	
	Self etch Gluma prior to etching	80	106.20	
	Self etch Gluma after etching	76	147.55	
	Total	504		
Post Op sensitivity 24hr VAS	Total etch control	86	125.47	0.126
	Total etch Gluma prior to etching	94	122.94	
	Total etch Gluma after etching	86	117.62	
	Self etch control	82	136.49	

	Self etch Gluma prior to etching	80	125.30	
	Self etch Gluma after etching	76	132.62	
	Total	504		
Post Op sensitivity 48hr VAS	Total etch control	86	131.74	0.050
	Total etch Gluma prior to etching	94	127.98	
	Total etch Gluma after etching	86	123.48	
	Self etch control		132.76	
	Self etch Gluma prior to etching	80	114.36	
	Self etch Gluma after etching	76	128.18	
	Total	504		
Post Op sensitivity 1 week VAS	Total etch control	86	124.24	0.013
	Total etch Gluma prior to etching	94	130.96	
	Total etch Gluma after etching	86	124.38	
	Self etch control	82	129.76	
	Self etch Gluma prior to etching	80	115.00	
	Self etch Gluma after etching	76	134.53	
	Total	504		

p < 0.05 denotes statistically significant difference. All the values exhibit non – statistically significant difference. Statistical test applied *

Kruskal – Wallis test

Ranks

	Desensitizer Group	N	Mean Rank	*P Value
Pre Op VAS	Total etch control	86	36.83	0.012
	Self etch control	82	48.45	

	Total	168		
Post Op sensitivity 24hr VAS	Total etch control	86	40.67	0.337
	Self etch control	82	44.41	
	Total	168		

p< 0.05 denotes statistically significant difference. All the values exhibit non – statistically significant difference except the pre operative pain scores. Statistical test applied * Mann Whitney U test

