DESINSENSITIZING AGENT	Pre Op VAS	Post Op VAS (24 hrs)	Post Op VAS (48 hrs)	Post Op VAS (1 week)
	Mean±SD	Mean±SD	Mean±SD	Mean±SD
Total etch control	0.86±1.67	0.37±1.05	0.37±1.05	0.21±0.77
Total etch Gluma prior to etching	1.72±2.15	0.49±1.33	0.40±1.12	0.23±0.81
Total etch Gluma after etching	1.16±2.07	0.28±0.93	0.28±0.93	0.26±0.95
Self etch control	1.88±2.25	0.66±1.32	0.41±1.00	0.12±0.33
Self etch Gluma prior to etching	0.63±1.05	0.20±0.46	0.03±0.16	0.08±0.27
Self etch Gluma after etching	2.11±2.40	0.61±1.31	0.37±0.97	0.21±0.53

- **ESTIMATION PARAMETER:** Mean Difference (Final Values)

ESTIMATED VALUE:

The mean post-operative sensitivity at 1 week was 0.18 units lower in the **Self-etch Gluma prior to etching** group compared to the **Total etch Gluma after etching** group, indicating that the former resulted in reduced sensitivity following restoration.

CONFIDENCE INTERVAL: 95%

NUMBER OF SIDES: 1 – sided

LOWER LIMIT:

Estimation Parameter: Mean Difference (Final Values)

Estimated Value: +0.18

Lower Limit (95% CI, one-sided): +0.003

Parameter Dispersion Type: Standard Deviation

Dispersion Value: 0.1077

The dispersion represents the standard deviation of the difference in mean post-operative sensitivity between the two groups.

Age limits: Patient aged between 15 to 70 years of both the gender were included

Healthy volunteers only/ with disease and why: The reason only healthy individuals are often enrolled because this helps to ensure that any observed effects are specifically related to dentin hypersensitivity and not influenced by other factors, such as an impaired immune response that could be present in individuals with certain systemic conditions.¹²

Investigator's Info:

First name: [name] **Middle name:** Nil **Last name:** [name]

Degree: MDS (Master of Dental Surgery)

[contact]

Email ID: [contact]

College Info: CSI College of Dental Sciences and Research, Madurai (CSICDSR)

(Affiliated under TN [name] University, Chennai, India)

Individual Patient sharing: Individual patient details are often not shared in this research due to concerns about privacy, confidentiality, and potential harm to participants, as well as practical and logistical challenges.¹³

References:

1. Porto I. Postoperative sensitivity on direct resin composite restorations: Clinical practice guidelines. *Indian J. Restor. Dent.* 2012; 1:1–12.

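### Post-operative VAS is compared between arms without adjusting for pre-operative VAS (arm means 0.63 to 2.11), and the pre-treatment score is counted as evidence for the arm named best

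*Combined protocol and SAP*

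**What the plan says.** In the SAP, under Procedure, the six-arm Kruskal-Wallis test "was used independently for each time point": pre-operative, 24 hours, 48 hours and 1 week. The stated reason is: "Since each time point represents a distinct clinical endpoint, a separate Kruskal-Wallis test was conducted for each". Pre-operative VAS is on that list and receives its own p-value (0.003). The same section says that the self-etch Gluma prior to etching arm had the lowest VAS scores "at all time points, suggesting reduced post-operative sensitivity in this group".

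The effect estimate after the table of means is a difference in final values at 1 week: 0.18 between that arm and total-etch Gluma after etching, with a one-sided 95% lower limit of +0.003. The SAP reads it as "indicating that the former resulted in reduced sensitivity following restoration".

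No section mentions a covariate, a change score, ANCOVA or stratification by pre-operative VAS.

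**The concern.** The Procedure section gives VAS as the measure at all four times, so the baseline is the same measure as the outcome. Its arm means span 0.63 to 2.11, while the 1-week means span only 0.08 to 0.26. A baseline gap of that size on the outcome scale is the reason to adjust; the baseline p-value is not. If pre-operative sensitivity carries over, an unadjusted comparison favours arms that started low, and the arm named best has the lowest pre-operative mean.

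There is also an error of inference that does not depend on any correlation: a pre-treatment score is used as support for a treatment effect.

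Two conclusions are exposed: the best-arm statement, and the causal reading of the 0.18 difference.

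**Working it through.** **Inputs.** Ns and mean ranks come from the SAP Ranks tables; means and SDs from the SAP table of means; the estimate, dispersion and limit from the SAP estimation entries. The within-arm pre/post correlation ρ is not given, so 0.1, 0.3 and 0.5 are assumptions.

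**1. The plan's own figure.** Difference = 0.26 - 0.08 = 0.18. SE = √(0.95²/86 + 0.27²/80) = 0.1068 at the printed Ns, and 0.1078 at 84 per arm; the printed value is 0.1077. Limit = 0.18 - 1.645 × 0.1077 = +0.003. The figure reproduces.

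**2. Which N.** Mean ranks weighted by N must average (N + 1)/2, which is 252.5 for N = 504. The printed ranks average 126.5 at all four times, which fits N = 252. The two-control table, printed as 168, averages 42.5, which fits 84. With arms halved to 43 and 40, SE = √(0.95²/43 + 0.27²/40) = 0.151 and the unadjusted limit is 0.18 - 1.645 × 0.151 = -0.068. Both cases are carried forward.

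**3. Is the named arm lowest throughout?** By means, yes. By the ranks that the SAP tests, no:

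| Time | Named arm's mean rank | Arms below it |
|---|---|---|
| Pre-op | 106.20 | total-etch control 105.48 |
| 24 h | 125.30 | total-etch Gluma after 117.62; total-etch Gluma prior 122.94 |
| 48 h | 114.36 | none |
| 1 week | 115.00 | none |

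**4. The 0.18 after adjustment.** The baseline gap is 1.16 - 0.63 = 0.53. Pooled six-arm SDs are 1.984 pre-op, 1.114 at 24 h, 0.937 at 48 h and 0.670 at 1 week. With a common linear slope b = ρ × SDpost/SDpre, the adjusted difference is 0.18 - 0.53b, its SE is multiplied by √(1 - ρ²), and the limit is the difference minus 1.645 SE. SE inflation from baseline imbalance is ignored.

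| ρ | b | Difference | Limit, N 504 | Limit, N 252 |
|---|---|---|---|---|
| 0 | 0 | 0.180 | +0.003 | -0.068 |
| 0.1 | 0.034 | 0.162 | -0.014 | -0.085 |
| 0.3 | 0.101 | 0.126 | -0.043 | -0.111 |
| 0.5 | 0.169 | 0.090 | -0.063 | -0.125 |

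With the SDs of these two arms only (1.659 pre-op, 0.709 at 1 week), the differences at ρ = 0.1, 0.3 and 0.5 are 0.157, 0.112 and 0.067. The limits are -0.019, -0.057 and -0.087 at 504, and -0.090, -0.125 and -0.148 at 252.

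**5. Correlation at which another arm draws level.** This is the post-operative mean gap ÷ (SDpost/SDpre × baseline gap).

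| Time, comparator | Mean gap | Baseline gap | ρ, six-arm SDs | ρ, two-arm SDs |
|---|---|---|---|---|
| 24 h, total-etch Gluma after | 0.08 | 0.53 | 0.269 | 0.338 |
| 48 h, self-etch Gluma after | 0.34 | 1.48 | 0.486 | 0.614 |
| 1 week, self-etch control | 0.04 | 1.25 | 0.095 | 0.187 |

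These are the comparators that catch up first. Against total-etch control (baseline gap 0.23) the values are 1.32 and 1.27 at 24 h, 3.13 and 2.72 at 48 h, and 1.67 and 1.36 at 1 week. All exceed 1, so no correlation removes that lead.

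**6. Arm-level pattern.** This is six points and descriptive only. Correlation of pre-operative with post-operative arm means is 0.92, 0.72 and 0.24 at 24 h, 48 h and 1 week (0.87, 0.50 and -0.42 without the named arm). For mean ranks it is 0.56, 0.49 and 0.88 (0.60, 0.11 and 0.94 without it). At 1 week the answer depends on the scale, so the pattern neither establishes nor excludes confounding by baseline.

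**The case against.** An unadjusted comparison of randomised arms is not invalid in itself, and the correlation on which every adjusted figure depends is unknown. That stands: the figures show fragility and are not a corrected effect.

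At N = 252 it is the sample size, not baseline, that takes the limit below zero. That also stands.

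The small leads were never distinguishable from chance. The 1-week lead over self-etch control is 0.04 with an SE of about 0.047 at the printed N, and the 24 h lead over total-etch Gluma after is 0.08 with an SE of about 0.11. This is fair, but it weakens the best-arm statement further.

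A common linear slope is doubtful where scores sit near zero (48 h, named arm: 0.03 ± 0.16). This is accepted, and it is why a rank method is proposed.

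The lowest-score sentence follows a mention of means, and it is true of the means. Agreed; the rank order shows only that the SAP's own test scale does not agree at two of the four times.

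The Brief Summary and Outcome Measures put the 1-week assessment on the Schiff scale. If the tabled 1-week figures are Schiff scores, the same-measure argument fails at that time point. The Procedure section says VAS, and the conflict has to be settled first.

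None of this supplies the missing adjustment or lets a pre-operative score count as benefit.

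**Conclusion.** The concern holds. Two parts are certain from the text: no between-arm comparison uses pre-operative VAS, and that score is counted as support for reduced post-operative sensitivity.

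The numerical consequence is uncertain. Under a linear common slope and assumed correlations of 0.1 to 0.5, the 0.18 difference shrinks to between 0.16 and 0.09 (0.07 with two-arm SDs). At the printed N even a correlation of 0.1 takes the lower limit below zero. The named arm's lead in means is lost at a correlation of about 0.1 to 0.2 at 1 week, 0.27 to 0.34 at 24 h and 0.5 to 0.6 at 48 h. Its lead over total-etch control survives at any correlation. The best-arm and reduced-sensitivity conclusions should not stand as written.

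**What to change.** Reconcile three things first:
- the printed N of 504 (and 168) with ranks that fit 252 (and 84);
- who has a pre-operative VAS, since the outcome schedule lists only 24 h, 48 h and 1 week;
- whether the 1-week score is Schiff or VAS.

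Then:
- Rerun each post-operative comparison with pre-operative VAS as a covariate, for example by rank ANCOVA.
- Give a baseline-adjusted mean difference with a bootstrap or robust interval beside the unadjusted one, and report the within-arm correlation. Label this analysis as added after results were known.
- Report pre-operative VAS as a baseline description, not an endpoint, and remove it from the lowest-at-every-time argument.
- Restate the best-arm and reduced-sensitivity conclusions from the adjusted results, and say where means and ranks order the arms differently.

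The statement that "most treatment protocols were non-inferior" should be withdrawn for a separate reason: its reference arm was chosen from the data and no margin is stated. Adjustment does not repair that.

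The cost is small: a rerun and text edits on data already collected, once the three reconciliations are done. Covariate adjustment would not repair a failed allocation, should the reconciliation reveal one.
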